- 5.2.1.8 Once MTD is defined, the RP2D will be selected based on efficacy and safety result from the phase I in discussion with the PI and the sponsor. The Investigator is responsible for completing the cohort summary template prior to advancing subjects to the phase II portion. Any patients still on study from the phase I portion at a dose lower than RP2D can be dose escalated up to RP2D. However, the dose for any patient may never exceed the RP2D.

- 5.2.2 One cycle of therapy is defined as 28 days. Patients will receive one cycle of therapy every 28 days (+/- 5 days).
- 5.2.2.1 In the phase II portion of the study (once the MTD dose has been defined) cycles may be started early (but not earlier than day 23) for patients with active disease if judged in the best interest of the patient.
For the lead-in cohort, DLT defining period is 28 days. As such, cycle 2 should not be started before 28 days for the patients being treated on the lead-in cohort.
- 5.2.2.2 Subsequent cycles may be delayed for recovery of toxicity or other medical conditions (e.g. infections). Delays in start of subsequent cycles greater than 8 weeks will be acceptable only for patients who are deriving clinical benefit and after discussion with the principal investigator of potential risk/benefit ratio and clear documentation in the medical record of the reason for continuation and perceived benefit to the patient from continuation of this therapy.
- 5.2.2.3 In instances where one drug has to be discontinued transiently because of safety, the administration of the other drug may continue as scheduled.
- 5.2.2.4 Azacitidine and avelumab will be held during phase II of the study, for grade 4 neutropenia or grade 4 thrombocytopenia lasting ≥ 42 days from the start of each cycle, in the absence of evidence of active AML. If prolonged grade 4 neutropenia (more than 42 days) WITH evidence of a hypocellular marrow (marrow cellularity less than 5% without evidence of leukemia) is observed, 5-azacytidine and avelumab will be discontinued. Delays in start of subsequent cycles greater than 42 days will be acceptable only for patients who are deriving clinical benefit and after discussion with the principal investigator of potential risk/benefit ratio.

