5.4 Duration of Therapy

In the absence of treatment delays due to adverse events, treatment may continue until one of the following criteria applies:

1. Clinically significant progressive disease, or
2. Intercurrent illness that prevents further administration of either treatment agent, or
3. Patient request, or
4. General or specific changes in the patient's condition render the patient unacceptable for further treatment in the judgment of the investigator, or
5. Unacceptable toxicity that in the opinion of the investigator makes it unsafe to continue therapy.

5.4.1 It is planned that up to a total of 24 cycles of therapy will be administered for patients deriving benefit from this regimen. Continuation of therapy for patients completing 24 cycles of therapy may be considered on a case- by-case basis after discussion with the principal investigator and IND Office.

5.4.2. A minimum of 1 full course (defined as the administration of 5- azacytidine for 7 days and one dose of avelumab) will be required for a patient to be considered as having received an adequate trial to evaluate efficacy. All patients receiving at least one dose of any of the two drugs will be considered evaluable for toxicity.

5.5 Supportive Care:

Supportive care measures including blood products, infection prophylaxis and growth factors will be administered according to institutional and MDACC Leukemia Department guidelines.

Management Algorithms for Treatment of Avelumab Related Adverse Events

Immuno-oncology (I-O) agents are associated with AEs that can differ in severity and duration than AEs caused by other therapeutic classes. Avelumab is considered an immuno-oncology agent in this protocol. Early recognition and management of AEs associated with immuno-oncology agents such as avelumab may mitigate severe toxicity. Avelumab has a known safety profile however, a general principle is that differential diagnoses should be diligently evaluated according to standard medical practice. Non- inflammatory etiologies should be considered and appropriately treated. Corticosteroids are a primary therapy for immuno-oncology drug-related adverse events, and avelumab is no exception. The oral equivalent of the recommended IV doses may be considered for ambulatory patients with low-grade toxicities. The lower bioavailability of oral corticosteroids should be taken into account when switching to the equivalent dose of oral corticosteroids.

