is unable to return to MDACC the follow-up visits may be conducted via telephone. Every 3-6 months for up to 5 years after last dose of study drug patient will have a physical exam and blood (about 1-2 teaspoons) will be drawn for routine testing. If the patient is unable to return to MD Anderson, they may be called by a member of the research staff and asked how they are feeling.

Table 6. The study assessment schema is shown in tabular form below

Study Period/Cycle	Screening*	Treatment																	End of Study (EOS) ^{h,i}	Long-Term Follow-Up	
		Cycle 1						Cycle 2						Cycle 3							Subsequent Cycles ^k
Cycle Day		1	8	14	15	22	28	1	8	14	15	22	28	1	8	14	15	22	1	30 Days After Last Dose	Every 3-6 months
Study Day	-14 to 0	1	8		15	22		29	36		43	50		57	64	70	71	78	—		
Complete history	X	X						X						X					X		
Physical examination ^a	X	X						X						X					X	X	
Vital Signs ^{**}		X		X				X		X				X		X			X		
Performance status	X	X						X						X					X	X	
Document all measurable disease (if present)	X																				
Concomitant medications ^a	X	X						X						X					X		X
ECG ^l	X							X						X					X		
CBC with differential ^b	X	X	X		X	X		X	X		X	X		X	X		X	X	X	X	
Sodium, Potassium, Chloride, glucose, uric acid, bicarbonate, BUN, Creatinine, total bilirubin, direct bilirubin, calcium, magnesium, ALT ₇ or AST, alk phos ^b	X	X	X		X	X		X	X		X	X		X	X		X	X	X	X	
Routine Urinalysis	X	X						X						X					X		
TSH, free T3, free T4 ^c , free & total cortisol		X						X						X					X		
Pregnancy test ^d	X																				
Bone marrow aspirate/biopsy ^e	X						X												X		

Correlative	Screening	Cycle 1				Cycle 2				Cycle 3				Subsequent cycles	EOS
Optional correlatives on blood ^f	X			Day 14	Day 21-28			Day 14		No		No		Day 1 and 14 of cycles 4, 8, 12	If possible
Chest X-ray	X														
Respiratory PCR panel	X														
Optional correlatives on bone marrow ^g	X				C#1 Day 28			C#2 Day 28				C#3Day 28	Day 28 of cycle 6, 12	If possible	

* Samples collected at screening do not need to be repeated on Day 1 of Cycle 1.

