8.1 Discontinuation Criteria for Individual Patients

9.1.1 Patient Withdrawal

Patients may voluntarily withdraw consent to participate in the clinical study at any time and without giving any reason. Their withdrawal will not jeopardize their relationship with their healthcare providers or affect their future care. Patients may also choose to withdraw from study treatment, but agree to remain in the study for follow-up procedures.

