11.1 Sample Size

Part a. Lead-in phase IB

The primary objective of the lead-in phase is to determine the MTD and DLT of avelumab in combination with 5-azacytidine in patients with refractory/ relapsed AML during the first cycle (28 days). 12 - 18 participants will be accrued into lead-in part of the study.

Once safety of the MTD has been established, any patients still on study at a dose lower than MTD can be dose escalated up to MTD.

Part b. Phase II

The primary objective of the phase II is to determine the efficacy of avelumab in combination with 5-azacytidine in patients with refractory/relapsed or untreated AML. The efficacy of the combination will be measured by the overall response rate (ORR), defined as CR (complete remission) + CR_p (complete remission with incomplete platelet recovery) + CR_i (complete remission with incomplete count recovery) + PR (partial response) + morphologic leukemia free state (MLFS)+HI within 3 months of treatment initiation among adult patients with refractory/ relapsed AML. ORR and toxicity will be monitored simultaneously using the Bayesian approach of Thall, Simon, Estey (1995, 1996) and the extension by Thall and Sung (1998).

Up to 40 additional patients (excluding patients treated at the MTD from the lead-in part) will be recruited for the Phase II part.

Total accrual: 12-18 patients from lead-in + 40 Phase II patients (N= 52 - 58 patients)

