where $P(\text{ORR}, E)$ and $P(\text{TOX}, E)$ are the true ORR and toxicity rates for the combination treatment, and $p(\text{ORR}, H)$ is the true ORR rate of the standard treatment. The first rule provides for stopping the study if the data suggest that it is unlikely (i.e., probability < 2.5%) that ORR rate of the combination treatment is greater than the ORR rate of standard treatment by 20.0%. The second condition will stop the study early if excessive therapy-related grade 3/4 toxicity (>30%) is highly probable (i.e., probability >97.5%) for the combination treatment. Monitoring for toxicity and fertility will not begin until 5 patients have been evaluated, and cohort size for future evaluations is 5.

The monitoring rule for the toxicity rate, based on these assumptions and monitoring conditions above is found in Table 7. **For example, accrual will cease if 4 or more patients experience toxicities among the first 5 patients.**

Table 7. Stop accrual if the number of drug-related grade 3/4 toxicities is greater than or equal to indicated (i.e., # patients with toxicities) among the number of patients evaluated								
# patients evaluated	5	10	15	20	25	30	35	40
# patients with toxicities	4-5	7-10	9-15	11-20	13-25	15-30	17-35	Always stop

Monitoring the ORR rate, based on the above assumptions and monitoring conditions is found in Table 8. **For example, accrual will cease if no patients experience an overall response within 3 months of initiation of therapy in the first 10 patients treated.**

Table 8. Stop accrual if the number with overall response is less than or equal to indicated (i.e., # patients with overall response) among the number of patients evaluated							
# patients evaluated	5-10	15	20	25	30	35	40

# patients with overall response	0	0-1	0-2	0-3	0-4	0-5	Always stop
----------------------------------	---	-----	-----	-----	-----	-----	-------------

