All patients who received any dose of the study agent will be included in the analysis for efficacy and safety. Demographic/clinical characteristics (including duration of response) and safety data of the patients will be summarized using descriptive statistics such as mean, standard deviation, median and range. For the primary efficacy analysis, we will estimate the ORR for the combination treatment, along with the 95% credible interval. For the efficacy, a sample size of 40 patients ensures a posterior 95% credible interval for ORR of (0.17, 0.43), if the trial is not terminated early, under the assumption of a 30% ORR. Patients who drop out of the study before completing all the cycles will be treated as “failures” for the primary analysis. ORR during the study period will also be presented with the 95% confidence credible. The association between ORR and patient’s clinical characteristics will be examined by Wilcoxon’s rank sum test or Fisher’s exact test, as appropriate. Toxicity type, severity and attribution will be summarized for each patient using frequency tables.

The distribution of time-to-event endpoints (DFS and OS) including overall survival and progression free survival will be estimated using the method of Kaplan and Meier. Comparisons of time-to-event endpoints by important subgroups will be made using the log-rank tests. Paired t-tests will be used to determine the immunological and molecular changes in the peripheral blood and bone marrow from baseline to the time of response, and to the time of disease progression. Correlation analysis (such as logistic regression analysis) will be conducted to determine the relationship between induction of hypomethylation / DNA damage and clinical response.

A Toxicity Summary will be submitted to the IND Office Medical Monitor, after the first three patients have completed their first cycle of study therapy or administration is

discontinued, whichever comes first, and every three evaluable patients thereafter during the Lead-in Phase IB.

An Efficacy/Toxicity Summary will be submitted every five evaluable patients during **Phase II**.

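### The drop-out rule for the primary ORR runs past the 3-month endpoint, so a documented responder who later leaves the study is recoded as a failure

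*Combined protocol and SAP*

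**What the plan says.** - **Endpoint.** Section 11.1, Part b, defines the primary ORR as response "within 3 months of treatment initiation among adult patients with refractory/ relapsed AML".
- **Monitoring.** Section 11.2 applies the same window to Table 8: "accrual will cease if no patients experience an overall response within 3 months of initiation of therapy in the first 10 patients treated". It attaches no drop-out condition to that count.
- **Drop-out rule.** The Statistical Analysis Plan text at the end of section 11.2 reads "Patients who drop out of the study before completing all the cycles will be treated as" failures, and says that this is for the primary analysis.
- **Second estimate.** The same paragraph adds "ORR during the study period will also be presented", so the whole-study rate is separate from the primary one.
- **Number of cycles.** No required number is given. Section 5.4.1 says "It is planned that up to a total of 24 cycles of therapy will be administered for patients deriving benefit from this regimen", and section 5.2.2 says "One cycle of therapy is defined as 28 days".
- **Who leaves the study.** Section 9.1.1 says "Patients may also choose to withdraw from study treatment, but agree to remain in the study for follow-up procedures". Section 9.1.4 keeps patients on study after treatment stops unless they withdraw consent for follow-up, die or are lost. Section 7.2.12 adds, for a responder after active treatment who "is unable to return to MDACC the follow-up visits may be conducted via telephone".

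**The concern.** A binary endpoint with a 3-month window is settled for each patient at 3 months. Counting a patient who leaves before then without a response as a failure is ordinary and conservative. The rule here goes further. It is tied to completing every cycle, a term the plan does not define, and it can reverse an outcome that has already been observed.

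The monitoring rule and the primary analysis can then classify the same patient in opposite ways. The primary ORR is what section 11.2 sets against the 30% target, so an understated figure bears on whether the regimen is judged worth pursuing. The study-period ORR might reveal a gap, but it does not correct the primary number.

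**Working it through.** **Inputs.** Response prior Beta(0.2, 1.8), n = 40, historical rate 10%, target 30% and futility cut-off 0.975 (all section 11.2); 3-month window (section 11.1); ceiling of 24 cycles (section 5.4.1); 28-day cycle (section 5.2.2). With x responders in 40 the posterior is Beta(0.2 + x, 41.8 − x). Intervals are equal-tailed.

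**Step 1: reproduce the plan's figures.** A 30% ORR is 12/40, giving Beta(12.2, 29.8) with 95% interval 0.165 to 0.435. The plan states (0.17, 0.43), which agrees. The Table 8 boundaries also reproduce. The largest x with P(ORR < 0.30) > 0.975 is 0, 0, 1, 2, 3, 4, 5 at n = 5, 10, 15, 20, 25, 30, 35.

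**Step 2: compare the two time limits.** Three months is about 91 days, or 91/28 = 3.25 cycles. The only planned total is 24 × 28 = 672 days. If completing every cycle means that ceiling, a responder still on treatment stays open to recoding for 672 − 91 = 581 days, about 19 months, after the endpoint is fixed. This is nominal: 24 is a ceiling, cycles may shift by 5 days, and the plan does not say that this is what it means.

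**Step 3: classify patients under each rule, read literally.**

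| Patient | Table 8 | Primary ORR |
|---|---|---|
| No response, leaves before 3 months | not a response | failure |
| Response by 3 months, stops treatment, stays in follow-up | response | response |
| Response by 3 months, later withdraws consent or is lost before completing the cycles | response | failure |
| Response by 3 months, later dies | response | not stated |

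The third row is the conflict. The fourth is open because section 9.1.4 lists death among the ways of ceasing to remain on study, while section 11.2 does not say whether it is a drop-out.

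**Step 4: effect on the estimate.** The plan gives no drop-out rate, so the number recoded is an assumed range. Each recoded responder costs 1/40 = 2.5 percentage points.

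| Recoded | Primary ORR | 95% interval | P(ORR < 0.10) |
|---|---|---|---|
| 0 | 12/40 = 30.0% | 0.165 to 0.435 | 0.0004 |
| 1 | 11/40 = 27.5% | 0.146 to 0.408 | 0.0014 |
| 2 | 10/40 = 25.0% | 0.127 to 0.382 | 0.0048 |
| 3 | 9/40 = 22.5% | 0.109 to 0.354 | 0.0147 |
| 4 | 8/40 = 20.0% | 0.092 to 0.326 | 0.04 |

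With up to three recoded, the interval stays above the 10% historical rate. With four, the lower limit falls below it. The count of 3-month responses is 12 in every row.

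**The case against.** The strongest reply is that the plan can be read more narrowly. The sentence concerns the primary analysis, that endpoint is limited to 3 months, and the whole-study ORR is presented separately. The rule could therefore mean leaving before completing the cycles inside the window. That reading is sensible, but the plan does not state it, and two analysts could code the same patient differently.

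A second reply is that Table 8 is silent on responders who have since left, so the conflict is partly inferred. It is true that no opposite rule is written out. But Table 8 counts response within 3 months without any condition, and a documented response meets that description.

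Third, little may turn on it. Table 8 governs accrual only and its last active look is at 35 patients, so recoding at the end changes no stopping decision. The plan sets no posterior-probability criterion at 40 patients that one or two recoded responders would flip. The group is narrow, and the numbers recoded are assumed. All of this stands. It limits the consequence but does not remove the miscount.

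**Conclusion.** The rule is wrong as written and should be fixed. Followed literally, it recodes observed responders as failures for an endpoint that was already determined, and it breaks the match between the primary ORR and the count that Table 8 monitors.

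The direction is certain: downward only. The size is unknown and probably modest, at 2.5 percentage points per recoded responder out of 40. The conclusion rests on the literal wording and on the absence of any text limiting the rule to 3 months. It does not depend on the 24-cycle reading, which affects only how long a responder stays exposed. The narrowness of the group assumes that a later death is not a drop-out; if it is, the group is larger.

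**What to change.** Replace the drop-out sentence in the Statistical Analysis Plan part of section 11.2 with wording such as:

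> Patients without a documented qualifying response within 3 months of treatment initiation, for any reason including drop-out, are counted as failures in the primary analysis; later departure from the study does not undo a documented response.

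State that Table 8 uses the same response count, and that a later death is treated as later departure. Early drop-outs without a response remain failures, so the conservative part of the rule is kept. The stated (0.17, 0.43) interval and the Table 8 boundaries do not change. The cost is a short text change in the SAP, with no extra data, visits or patients.

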12.0 PROTOCOL ADMINISTRATION

This study will be monitored by the MD Anderson IND Office and a protocol-specific monitoring plan will be followed.

Protocol amendments

Changes to the protocol will be made only when protocol amendments have been signed by the principal investigator and approved by Pfizer and the IRB of the study center.

Archival of data

MD Anderson-IND study must retain all records *indefinitely*.

